### **2.12.2. Final Follow-Up Evaluation; Required: 12 Weeks ( $\pm$ 3 weeks) after final treatment visit**

[figure not shown]
The following evaluations will be performed at the final post-treatment follow-up visit:

ZELTIQ P/N: [REDACTED]  
Protocol Number: ZA17-005

This document and the contents hereof are considered proprietary and confidential information of ZELTIQ Aesthetics, Inc. Disclosure to unauthorized individuals or dissemination, publication or copying is prohibited without prior written consent of ZELTIQ.

1. Obtain Subject Self-Rating Scale score.
2. Obtain weight.
3. The same evaluating investigator from prior visits will assess treatment area and determine severity of submental fullness based on CR-SMFRS score at this visit.
4. Photograph the treatment area using the same custom standardized setup and settings as the pre-treatment photographs.
5. Measure the fat layer thickness of the treatment site with a commercially available ultrasound device.
6. Clinical assessment of the treatment area for any epidermal, dermal and subcutaneous findings (e.g., erythema, bruising, swelling, pigment changes) as well as alterations in sensation (e.g., numbness, tingling).
7. Examine the oral cavity for evidence of dry mouth.
8. Assess lower face motor nerve function.
9. Obtain adverse event information.

Figure 5 illustrates subject enrollment and study flow. Table 2 summarizes the study schedule and events at each visit.

**Figure 5. Subject enrollment and study flow.**

**Table 2. Schedule of assessments.**

	Screening (< 1 hr)	Treatment Visit 1 (< 3 hrs)	Treatment Visit 2 (< 3 hrs)	Treatment Visit 3 (< 3 hrs)	Treatment Visit 4 (Optional) (< 3 hrs)	2 Week Follow-Up (< 1 hr) †	Final Follow-Up (< 1 hr)
Time Frame	Day - 30 to 0	Day 0	6 ± 1 weeks post last tx	6 ± 1 weeks post last tx	4-7 weeks post last tx	2 weeks ± 3 days post each tx	12 ± 3 weeks post final tx
Informed Consent*	X						
Inclusion/Exclusion Criteria	X	X	X	X	X		
Pregnancy Test	X	X	X	X	X		
Medical History	X						
Tx Site Assessment	X	X	X	X	X	X	X
Oral Cavity Assessment	X		X	X	X	X	X
Nerve Function Assessment	X		X	X	X	X	X
Height	X						
Weight	X	X	X	X	X	X	X
CR-SMFRS Assessment	X			X	X		X
Photography	**X	X	**X	X	**X	**X	X
Ultrasound		X		X			X
CoolMini Treatment		X	X				
KYBELLA® Treatment				X	**X		
[REDACTED]		X	X	X	X	X	X
AE Assessment		X	X	X	X	X	X
Subject Self Rated Scale	X			X			X

\* Informed consent to be signed by subject prior to the collection of any data or completion of any study procedures.

\*\* Optional

† Follow-up after each treatment

## 2.13. Assessments

Study-related assessments are described below.

### 2.13.1. Safety Assessments

The primary safety endpoint is the incidence, seriousness, severity and duration of device, drug and/or procedure-related adverse events at the final follow-up visit. Safety will be monitored by documentation of adverse events and clinical assessment of the treatment site.

### 2.13.2. Clinician Evaluation using CR-SMFRS

The primary measure will be clinician live assessment of the patient's severity of submental fat as determined by the CR-SMFRS (Table 3). The CR-SMFRS score will be based on the investigator's clinical evaluation of the subject, including palpation of the chin and neck area; anterior, oblique, and profile views of the chin and neck; and observation of pronation, supination, and lateral movement of the head. The score will be determined using the rating scale definitions and the representative photographs associated with each score. The final score will be determined while the subject's head is in the Frankfort plane posture as described in the CR-SMFRS. The score will be recorded as a whole number.

**Table 3. Clinician Reported-Submental Fat Rating Scale (CR-SMFRS)**

Score	SMF Description
0	Absent Submental Convexity: No localized submental fat evident.
1	Mild Submental Convexity: Minimal, localized submental fat.
2	Moderate Submental Convexity: Prominent, localized submental fat.
3	Severe Submental Convexity: Marked, localized submental fat.
4	Extreme Submental Convexity.

### 2.13.3. Photography

Photography will be performed by a qualified representative of the sponsor.

A series of photos of the treatment areas will be obtained at the pre-treatment, prior to first KYBELLA® injection (Treatment visit 3) and final follow-up visits, using custom standardized setup, lighting, and camera settings to ensure consistency. All photographs will be captured at fixed angles and posture (Frankfort plane). Using a series of pre-determined markings on the floor, the photographer will position the camera at the pre-determined reference points to ensure that the reproduction ratio and focal

distance are maintained throughout the image series during the study. During follow-up visits, the photographer will re-align subjects by referencing baseline images.

#### **2.13.4. Ultrasound Measurements**

Ultrasounds will be performed by a qualified representative of the sponsor.

After treatment sites have been identified, the ultrasound measurement locations will be marked. Up to 3 measurement locations will be marked on the intended treatment area. A template may be created prior to treatment to mark the locations for ultrasound measurements. This template (transparency) will be created using external landmarks (e.g., skin imperfections) as reference points, identifying the peak of the bulge and the locations for ultrasound measurements. At follow-up visits, the template will be used to mark the locations for ultrasound measurements. A SonoSite TITAN® ultrasound system (or equivalent approved by Sponsor) will be used in this study. A high frequency linear transducer array (L38/10-5: 38-mm broadband, 10-5 MHz, optimized for breast, small parts, interventional, musculoskeletal and vascular imaging) provides sufficient spatial resolution to visualize anatomical features for image plane alignment for fat layer measurement. Stored images will be transferred to an off-line PC based image analysis tool for fat layer measurements. These files will be stored by the Sponsor and indexed by subject identifier. Standardized techniques for obtaining images will be used to ensure consistency throughout the study.

The individual(s) analyzing the images will be presented with two series of images for each measurement site, the pre-treatment and the final post-treatment series, and asked to measure the depth of fat layer in each image. The order in which the images are presented will be randomized by subject.

#### **2.13.5. Subject Self-Rating Scale (SSRS)**

Subject's assessment of overall satisfaction with their face and chin using the SSRS will be obtained at Screening (baseline score), at Treatment Visit 3 (prior to first KYBELLA® treatment) and at the final 12-week follow-up visit.

SSRS is a subject self-rating scale, scored on a 7-point scale with 0=extremely dissatisfied, 1=dissatisfied, 2=slightly dissatisfied, 3=neither satisfied nor dissatisfied, 4=slightly satisfied, 5=satisfied, and 6=extremely satisfied.

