## 2. Study Protocol

## 2.1. *Design*

## Prospective, controlled, open-label, interventional study.

## 2.2. *Study Duration*

Enrollment and follow-up is expected to take up to nine (9) months for each subject.

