**Table 1. Eligibility criteria.**

### **Inclusion Criteria**

- a) Male or female subjects  $\geq$  22 years of age and  $\leq$  65 years of age.
- b) Women of childbearing potential must have a negative urine pregnancy test result at screening and agree to practice adequate contraception.
- c) CR-SMFRS grade of 4 (extreme) as determined by the evaluating investigator at screening.
- d) Dissatisfaction with the submental area expressed by the subject as a rating of 0, 1 or 2 using the Subject Self Rating Scale (SSRS) as determined at Screening visit.
- e) History of stable body weight confirmed by the subject, for at least 6 months prior to the first treatment session.
- f) Subject agrees to maintain his/her weight (i.e., within 5%) by not making any major changes in their diet or exercise routine during the course of the study.
- g) Subject agrees to forgo any treatment or behavior (e.g., unshaven facial hair) during the subject's participation in the study that may affect the assessments of the submental area.
- h) Subject is medically able to undergo the administration of KYBELLA® determined after review of the subject's medical history for which the evaluating investigator identifies no clinically significant abnormality.
- i) Subject has read and signed the study written informed consent form.

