### 2.14.2. **Secondary Endpoints**

Secondary endpoints in the study are as follows:

1. Reduction in fat layer thickness, as measured by ultrasound at Week 12 post-final treatment.
2. Subject satisfaction as assessed by Subject Self-Rating Scale scores.

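### The Screening SSRS is both the entry filter and the baseline, so any change in satisfaction is expected to include some upward regression to the mean, of a size the documents do not fix

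*Combined protocol and SAP*

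**What the plan says.** Inclusion criterion d (Table 1) requires "Dissatisfaction with the submental area expressed by the subject as a rating of 0, 1 or 2" on the SSRS, "as determined at Screening visit". The scale is "scored on a 7-point scale with 0=extremely dissatisfied" and runs up to 6, so entry is limited to the lowest three of seven categories.

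Section 2.13.5 labels the Screening rating as the baseline: the SSRS rating "using the SSRS will be obtained at Screening (baseline score), at Treatment Visit 3 (prior to first KYBELLA® treatment" is followed by one at the final visit. The row "Subject Self Rated Scale" in Table 2 agrees, with marks at Screening, Treatment Visit 3 and Final Follow-Up only. The steps for Treatment Visit 1 in section 2.11.1 include weight, baseline photographs and ultrasound, but no SSRS.

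The secondary endpoint in section 2.14.2 reads "Subject satisfaction as assessed by Subject Self-Rating Scale scores". It names no metric. No text is visible under heading 2.15.3.4, which may reflect redaction.

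Section 2.1 describes a "Prospective, controlled, open-label, interventional study", but section 1.1 describes one treatment sequence for all subjects, and no untreated or comparison group appears.

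**The concern.** A self-rating is not perfectly repeatable. If only low ratings are admitted, the group includes some people whose Screening answer was lower than their usual level. On the next occasion their answers move back up on average, whether or not treatment has done anything. When the rating used for selection is also the baseline, that movement is counted as change.

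A concurrent control group would show the same movement and allow it to be subtracted. A second pre-treatment rating would show how large it is. The plan has neither, so part of any reported gain in satisfaction could come from the entry rule, and it could not be separated afterwards.

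**Working it through.** **Plan's own figure.** There is none to reproduce. The plan gives no expected SSRS change, SD or reliability, and the sample size of up to 20 (sections 2.6 and 2.15.3.5) is a feasibility choice.

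**Inputs from the documents.** Scale 0 to 6; eligible if Screening SSRS is 2 or less; baseline is the Screening SSRS; no rating on Day 0.

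**Assumed inputs.** Mean of the candidates' latent score before selection, 0.5 to 2.5; SD 1.2; test-retest correlation r, 0.6 to 0.8; zero treatment effect.

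**Step 1, closed form.** For a continuous score selected below a cut, expected rise = (1 − r) × SD × φ(c)/Φ(c), with c = (2.5 − mean)/SD. The cut is 2.5 because scores are whole numbers. At mean 2.0 and r = 0.7:

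- c = (2.5 − 2.0)/1.2 = 0.417
- φ(c)/Φ(c) = 0.366/0.661 = 0.553
- expected rise = 0.3 × 1.2 × 0.553 = 0.20 points

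The rise is zero only if r = 1, so the direction does not depend on the other assumptions.

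**Step 2, simulation on the real scale.** Each person has a fixed true value plus independent error at each occasion. Scores are rounded and limited to 0 to 6, and a person is kept if the first score is 2 or less (2,000,000 draws per scenario). At mean 2.0 and r = 0.7 the rise is +0.24, somewhat above the closed form, as expected when rounding adds error. Ranges below run over r = 0.8 to 0.6.

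| Candidate mean | Share eligible | Expected drift, no effect | Later score 3 or more | Later score 4 or more |
|---|---|---|---|---|
| 0.5 | 95% | +0.03 to +0.06 | 2.5–3.5% | under 1% |
| 1.0 | 89% | +0.06 to +0.11 | 5–7% | under 1% |
| 1.5 | 80% | +0.11 to +0.20 | 9–13% | 0.6–1.9% |
| 2.0 | 66% | +0.17 to +0.30 | 14–20% | 1.2–3.7% |
| 2.5 | 50% | +0.25 to +0.44 | about 20–29% | 2.1–6.5% |

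**Step 3, wider assumptions.** With mean 0.5 and SD 1.0 (about 98% eligible), the drift is 0.01 to 0.03 for r from 0.9 to 0.5. With mean 3 and SD 1.25 (about 35% eligible), it is 0.21 to 0.74 over the same r.

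**Step 4, effect on a test.** Suppose change were tested by a paired t-test at two-sided 0.05 with 20 subjects, which the visible plan does not say. With SD 1.25 and r from 0.9 to 0.5, the chance of a significant rise with no effect is 4–8% at candidate mean 1 and 10–29% at mean 2. The nominal figure in that direction is 2.5%.

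**Step 5, a Day 0 baseline.** If Day 0 errors are independent of Screening errors, the expected change from Day 0 is 0.00. If the two errors correlate at 0.5 (mean 2.0, r = 0.7), about +0.10 of the +0.24 remains. If they correlate fully, all of it remains.

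**The case against.** The strongest objection is that the affected analysis is inferred. Section 2.14.2 gives no metric and the analysis text under 2.15.3.4 is not visible, so the plan may report the proportion satisfied at the final visit, which is little affected. This stands as a condition on the point. Calling the Screening score the baseline makes a change analysis the natural reading, but does not establish it.

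The second objection is that the drift may be negligible. Section 2.5 recruits people who want submental fat reduced, and Table 1 requires CR-SMFRS grade 4. Most such candidates may rate 0 to 2 anyway, and the filter then removes few of them. This also stands. Candidate means of 1.5 to 2.5 imply that 20% to 50% of candidates fail criterion d, and the documents do not show whether that is so.

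Three stronger readings are tempting and are not supported:

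- **That mean satisfaction will rise without treatment.** Only the expected mean rises. An observed mean in at most 20 subjects need not.
- **That up to about 29% would count as successes with no effect.** That figure uses a cut of 3, the neutral midpoint, which the plan does not define as success. At 4 or more the figure is at most about 7%.
- **That a Day 0 score removes the problem entirely.** That requires independent errors. Section 2.9.1 and Table 2 let Screening fall as late as Day 0, so a subject may not make a separate untreated visit, and a same-day repeat may recover little.

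Finally, this is a secondary endpoint in an open-label feasibility study, and expectation effects on a self-rating would remain after any change of baseline. That limits the importance of the point, not its correctness.

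**Conclusion.** The point holds as an expected bias of uncertain size. The same Screening rating selects subjects and serves as baseline, with no second pre-treatment rating and no comparison group. Any mean change in SSRS from that baseline therefore has an expected upward component unrelated to treatment, for any rating that is less than perfectly repeatable.

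Under the assumptions of SD 1.2 and r of 0.6 to 0.8, that component is between about +0.03 and +0.44 points on the seven-point scale, depending mainly on how many candidates the filter excludes. The documents do not say where in that range the trial lies. The conclusion is conditional on a change-from-baseline analysis. It does not show that an observed gain would be spurious, and it does not touch the primary endpoints. It is a worthwhile improvement rather than a defect that threatens the study.

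**What to change.** 1. Add the SSRS at Treatment Visit 1, before cooling starts: one mark in Table 2 and one step in section 2.11.1.
2. In section 2.13.5, define the Day 0 score as the baseline for the satisfaction endpoint, and keep the Screening score for eligibility only.
3. Report the mean Screening-to-Day 0 change as an estimate of the drift, together with the interval between the two ratings. For subjects screened on or close to Day 0, say that the repeat rating is less informative.
4. If the SSRS analysis does not already do so, state whether it is change from baseline, the proportion scoring 4 to 6 at the final visit, or both. If change is reported, say that without a control group it may still include some regression to the mean and open-label expectation effects.

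The cost is one seven-point question at a visit already scheduled, plus a few lines of text. The reported gain in satisfaction will probably be slightly smaller.

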## 2.14. **Endpoints**

The objective of this study is to evaluate the safety and efficacy of subcutaneous fat layer reduction in the submental area on subjects with extreme submental fullness defined by the CR-SMFRS as Grade 4 using CoolSculpting and KYBELLA® in sequence.

### 2.14.1. **Primary Endpoints**

The primary endpoints of the study will be defined as follows:

- Safety endpoint: incidence of device, drug or procedure-related adverse events.
- Efficacy endpoint:
  1. The reduction, from baseline (CR-SMFRS =4) to final follow-up, of submental fat (SMF) as assessed by the proportion of subjects who have at least a 1-grade improvement on the Clinician Reported Submental Fat Rating Scale (CR-SMFRS), and
  2. The reduction, from baseline (CR-SMFRS=4) to final follow-up, of SMF as assessed by the proportion of subjects who have at least a 2-grade improvement on the CR-SMFRS.

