## **2.9. *Screening Procedures***

### **2.9.1. *Screening Visit; Required; Week -4 to Day 0***

The subject shall be consented for study participation as described in Section 2.8. After the informed consent form is signed, subjects will be screened for eligibility. Each subject will be evaluated to determine that all eligibility criteria are met. The investigator or designee shall complete a brief medical history and examine the subject to confirm eligibility for the study.

1. Obtain Subject Self-Rating Scale score.
2. Obtain height and weight.
3. Evaluating investigator to assess intended treatment area and determine severity of submental fullness based on Clinician Reported-Submental Fat Rating Scale (CR-SMFRS).
  - a. Subjects must score a 4 (extreme) in order to be enrolled.
4. Assess oral cavity for current dental infection or evidence of dry mouth.
5. Assess function of the marginal mandibular nerve (grimace with ability to show lower teeth) and hypoglossal nerve (tongue does not deviate upon protrusion).

6. Assess upper neck to rule out enlarged lymph nodes or glands.
7. Assess for dermatological conditions that may lead to exclusion of the subject from the study.
8. Document subject's medication use (including over-the-counter medications, vitamins and herbs), Fitzpatrick Skin Type, and ethnicity, as well as any skin irregularities (e.g. moles, birth marks, scars, discoloration).
9. All female subjects of childbearing potential will be asked to take a pregnancy test (urine) prior to being treated. If the subject is pregnant, she will be excluded from participation.

Female subjects of childbearing potential will be advised to avoid becoming pregnant during the course of the study by agreeing to practice adequate contraception, in the judgement of the investigator, during the course of the study. If the subject becomes pregnant during the course of the study, she will not be treated subsequently with the study device or drug and she will be required to have follow-up photographs and ultrasounds. She will also be asked for information about the pregnancy and the birth of the child.

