### **2.11.1. Treatment Visit 1; Required; Day 0**

1. Review inclusion and exclusion criteria.

ZELTIQ P/N: [REDACTED]

Protocol Number: ZA17-005

2. Repeat pregnancy test for female subjects of childbearing potential (urine). Exclude subject from participation if the results are positive.
3. If the subjects meet all of the inclusion criteria and none of the exclusion criteria, then proceed with the study treatment.
4. Obtain weight
5. Obtain baseline photographs using custom standardized setup and settings.
6. Cleanse the treatment area with isopropyl alcohol.
7. Mark or outline the intended treatment area.
8. Measure the fat layer thickness of the intended treatment area with a commercially-available ultrasound device using a standardized protocol.

ZELTIQ P/N: [REDACTED]  
Protocol Number: ZA17-005

This document and the contents hereof are considered proprietary and confidential information of ZELTIQ Aesthetics, Inc. Disclosure to unauthorized individuals or dissemination, publication or copying is prohibited without prior written consent of ZELTIQ.

The investigator or staff will be present during the treatment to monitor the progress. Treatment may be discontinued due to subject discomfort or device malfunction. The need for post-treatment care is not expected for this study. Subjects will be encouraged to call the study site if they experience any unusual effects (e.g., severe discomfort or pain, severe and/or prolonged erythema, bruising, swelling, blistering, etc.). Refer to Section 6.2 for a listing of the expected side effects of the procedure.

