This document and the contents hereof are considered proprietary and confidential information of ZELTIQ Aesthetics, Inc. Disclosure to unauthorized individuals or dissemination, publication or copying is prohibited without prior written consent of ZELTIQ.

Potential Adverse Effect	Description
Vasovagal Symptoms	The occurrence of symptoms of anxiety, lightheadedness, dizziness, nausea, sweating, near syncope, or syncope (fainting).
Motor Nerve Injury	Injury to the lower face motor nerves such as marginal mandibular nerve (lower lip weakness) or hypoglossal nerve (tongue deviation).
Xerostomia	Injury to the submandibular gland as evidenced by the subjective decrease in saliva production.
Contour Irregularity	Significant indentation or contour irregularity in the treatment area that would require surgical intervention.
Allergic/Irritant Contact Dermatitis	Itchy rashes and skin peeling that may result from prolonged exposure to gel or applicator pressure
Subcutaneous Induration	Hardness within the treatment area, either as general firmness or discrete nodules. May present with pain and/or discomfort.
Paradoxical Hyperplasia	Visibly enlarged tissue volume within the treatment area which may develop 2-5 months after treatment. Surgical intervention may be required.
Other	Any other untoward medical event determined by the investigator to be an adverse event, regardless of the relationship to the device or treatment.

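### One screening CR-SMFRS score, which must be the scale maximum of 4, is both the entry gate and the primary baseline and is not repeated at Day 0, so rating error in subjects truly unchanged at 4 can only register as a one-grade response

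*Combined protocol and SAP*

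**What the plan says.** - **Entry.** Inclusion criterion c (Table 1) requires a "CR-SMFRS grade of 4 (extreme) as determined by the evaluating investigator at screening". Section 2.9.1 repeats the rule: "Subjects must score a 4 (extreme) in order to be enrolled".
- **Scale.** Table 3 runs from 0 to 4, and its top category is "Extreme Submental Convexity". Section 2.13.2 allows no half grades: "The score will be recorded as a whole number".
- **Baseline.** Section 2.14.1 fixes the baseline of both responder endpoints at 4. The first is the reduction "from baseline (CR-SMFRS =4) to final follow-up, of submental fat (SMF) as assessed by the proportion of subjects who have at least" a one-grade improvement, and the second requires two grades.
- **Timing.** The Table 2 row "CR-SMFRS Assessment" is marked at Screening, Treatment Visits 3 and 4 and Final Follow-Up, but not at Treatment Visit 1. Screening may precede Day 0 by about four weeks (30 days in Table 2).
- **Day 0.** Section 2.11.1 opens with "Review inclusion and exclusion criteria" and then lists weight, photographs and ultrasound, but no CR-SMFRS rating. Part of that section is missing from the public text, so the no-repeat reading rests mainly on Table 2. The criteria review does not imply a new rating, because criterion c refers to the screening score.
- **Rater and design.** The same evaluating investigator scores a given subject at every visit (section 2.3). The study is open-label (section 2.1); it is called controlled, but no control arm is described.

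**The concern.** Selecting subjects on one extreme score and reusing that score as baseline builds in regression toward lower scores. There are two routes.

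1. A subject who is truly grade 4 and stays there cannot be rated higher, so any error at follow-up shows as improvement.
2. A subject who is truly grade 3 but was rated 4 at screening shows a one-grade improvement as soon as the rating is correct.

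The scale also cannot record worsening. Section 6.2 lists paradoxical hyperplasia as a potential adverse effect ("Visibly enlarged tissue volume within the treatment area which may develop 2-5 months after treatment"), yet on this endpoint an enlarged submental area still scores 4 and looks like no change.

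With no comparator described, nothing in the planned data shows how often the same rater would score 4 and then 3 without treatment. The one-grade proportion is therefore hard to interpret, and it is a main efficacy output of a study meant to supply feasibility data (sections 1.1 and 2.15.3.5).

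**Working it through.** **Inputs from the documents.** N is at most 20 (section 2.6); baseline is 4 for everyone; scores are whole grades; the scale maximum is 4. Section 2.15.3.5 gives no effect size, null rate or precision target, so there is no planned figure to reproduce.

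**Assumptions, because the documents give no rating reliability.** All 20 subjects are evaluable. p is the chance that an untreated screened 4 is re-rated 3 or lower, taken as 5% to 30%. π is the true one-grade response rate.

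**Step 1. False one-grade responders.** Only subjects who do not truly respond can be false responders, so the expected number is 20 × (1 − π) × p.

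| p | π = 0 | π = 50% |
|---|---|---|
| 5% | 1 | 0.5 |
| 10% | 2 | 1 |
| 20% | 4 | 2 |
| 30% | 6 | 3 |

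**Step 2. Net bias.** Let each rating be off by one grade with probability e in each available direction. Take all true baselines as 4 and all true responders as finishing at grade 3. The observed one-grade rate is (1 − π)e + π(1 − e), so the bias is e(1 − 2π). More generally it is e × (share truly at 4 − share truly at 3). At e = 0.10:
- π = 30%: 0.7 × 0.1 + 0.3 × 0.9 = 34%, above the truth.
- π = 50%: 0.5 × 0.1 + 0.5 × 0.9 = 50%, no bias.
- π = 90%: 0.1 × 0.1 + 0.9 × 0.9 = 82%, below the truth.

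**Step 3. Adding selection at screening.** Let r be the ratio of true grade 3 to true grade 4 among candidates, assumed 0.5 to 2. The share of enrolled subjects who are truly grade 3 is f = re / [re + (1 − e)]. With no treatment effect, the false one-grade rate is (1 − f)e + f(1 − e), and the false two-grade rate is f × e. At e = 0.10:
- r = 0.5: f = 0.05/0.95 = 5.3%; one-grade 14.2% (2.8 of 20); two-grade 0.5%.
- r = 2: f = 0.20/1.10 = 18.2%; one-grade 24.5% (4.9 of 20); two-grade 1.8%.

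**Step 4. What a second rating does (same model, no treatment effect, e = 0.10).**
- Restricting to subjects rated 4 twice: the true grade 3 share becomes g = re² / [re² + (1 − e)²], which is 0.6% at r = 0.5 and 2.4% at r = 2. The false one-grade rate, (1 − g)e + g(1 − e), is 10.5% to 11.9%.
- Using the Day 0 score as baseline: a true 4 shows a false improvement with probability e(1 − e) = 9%. A true 3 does so with probability e(1 − e) + e(1 − 2e) = 17%. Weighting by f gives 0.947 × 9% + 0.053 × 17% = 9.4% at r = 0.5, and 0.818 × 9% + 0.182 × 17% = 10.5% at r = 2.

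Either way, the 14% to 25% range falls to about 9% to 12%. What is left is mostly error at the ceiling, which a repeat rating cannot remove.

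**Step 5. Precision.** If 2 of 20 were rated below 4 at Day 0, the exact 95% interval for the shift rate would be about 1% to 32%.

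**The case against.** A reader might infer that every one-grade rating error counts as a response, or that the one-grade rate must be inflated. The documents support neither. A subject truly improved to 3 but over-rated as 4 becomes a false non-responder, and Step 2 shows that the net bias turns downward when more subjects truly finish at 3 than at 4. It would also be wrong to say that 5 to 30 percentage points of the reported proportion are false. That range needs no true responders at all.

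A reader might also infer that enlargement would go unnoticed. It would not. Ultrasound is taken at Day 0, Visit 3 and Final Follow-Up, with image order randomised by subject (section 2.13.4); photographs are standardised (section 2.13.3); and adverse events enter the safety analysis (section 2.15.3.1). The limitation is confined to the primary scale.

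The plan has real mitigations: one rater per subject, a structured examination with reference photographs and fixed posture, and a two-grade endpoint that one-grade error barely touches. The study seeks feasibility data, and no success threshold is attached to the one-grade rate. A ceiling is inherent in studying extreme fullness. The age of the screening score is a minor matter: screening may fall on Day 0, and nothing in the documents suggests that fat changes over four weeks.

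The remedy also has limits. The rater knows that every enrolled subject scored 4, so a Day 0 rating is partly anchored. Making Day 0 the primary baseline would conflict with the fixed baseline of 4 in section 2.14.1 and change the meaning of a two-grade response (3 to 1 instead of 4 to 2 for some subjects). These points rule out a baseline switch in the primary analysis. They do not remove the case for a second rating.

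**Conclusion.** The concern stands in a bounded form. A single screening score at the scale maximum is both gate and baseline, with no repeat before treatment. Among subjects truly unchanged at 4, error goes one way only; subjects over-rated at screening add to the count; and worsening is invisible on this scale.

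Under the assumed re-rating probabilities of 5% to 30%, expected false one-grade responders are 1 to 6 of 20 with no true response and 0.5 to 3 at a 50% true response rate. The direction of the net bias depends on the true response rate and cannot be settled from the documents. The two-grade endpoint is affected far less. All of these sizes rest on assumed reliability. The structural facts come from Tables 1 to 3 and section 2.14.1.

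**What to change.** 1. Add a CR-SMFRS rating to Treatment Visit 1 (section 2.11.1 and Table 2), before treatment, by the same evaluating investigator, on a separate occasion from Screening where possible and without consulting the screening score.
2. Keep eligibility on the screening score and keep the primary definition with baseline 4. Say explicitly that the Day 0 rating alters neither.
3. Report the number rated below 4 at Day 0, with its exact confidence interval, beside the one-grade result.
4. Add a sensitivity analysis of both responder endpoints restricted to subjects rated 4 at both visits, or using the Day 0 score as baseline, and specify in advance which is used.
5. State in section 2.14.1 that worsening cannot be scored from a baseline of 4, and report how many subjects have greater ultrasound fat thickness at final follow-up than at Day 0.

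**Cost.** A few minutes at a visit already required, with no new staff; the ultrasound count uses data already planned. The re-rating is partly anchored, the shift rate is imprecise at N = 20, and the one-grade result may look less favourable.
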